6.3.4 Laboratory Data

Clinical laboratory tests on hematology, serum chemistry, electrolytes, and lipids and urinalysis will be performed according to the schedule in Section 3.6. Investigators will assess whether there are any clinically significant abnormalities and record the abnormality on medical history or AE forms.

Conversion to the International System of Units

All laboratory data will be stored in the database with the units in which they are originally reported. Laboratory data in summary tables and subject data listings will be presented in the International System of Units (SI units; *Système International d’Unités*). Laboratory data not reported in SI units will be converted to SI units before further processing or data analysis.

Abnormal Values

Based upon laboratory normal ranges, laboratory test results will be categorized according to the normal range as low, normal and high. Subjects with laboratory data outside the normal range will be listed with abnormal values flagged.

Table 3 Clinical Laboratory Tests

Hematology

Hematocrit (Hct)	Mean corpuscular volume (MCV)
Hemoglobin (Hgb)	Platelet count
Mean corpuscular hemoglobin (MCH)	Red blood cell (RBC) count
Mean corpuscular hemoglobin concentration (MCHC)	White blood cell (WBC) count with differential

Serum Chemistry, Electrolytes, and Lipids

Albumin (ALB)	Calcium (Ca)
Alanine aminotransferase (ALT)	Magnesium
Aspartate aminotransferase (AST)	Phosphorus
Blood urea nitrogen (BUN)	Potassium (K)
Glucose	Sodium (Na)
Total carbon dioxide	Total bilirubin
Creatinine	Direct bilirubin
Chloride (Cl)	Uric acid
Total protein	Low-density lipoprotein cholesterol (LDL-C), calculated
Total cholesterol (TC)	
High-density lipoprotein cholesterol (HDL-C)	
Triglycerides (TG)	

Urinalysis

Appearance	Nitrite
Bilirubin	pH
Color	Protein
Glucose	Specific gravity
Ketones	Urobilinogen
Microscopic examination of sediment	Leukocyte esterase
Occult blood	

Urine Collection

Glucose	Creatinine
---------	------------

Urine Drug Screen

Amphetamines	Opiates
Barbiturates	Benzodiazepines
Cocaine Metabolites	Cannabinoids
Cotinine	

Pregnancy Test

Infectious Disease Testing

Hepatitis B Surface Antigen (HbsAg)	Hepatitis C virus (HCV)
HIV	

6.3.5 Vital Signs

Vital signs include pulse (beats/min), SBP and DBP (mmHg), oral temperature (°C) and respiration rate (breaths/min).

Vital sign changes from baseline will be summarized by treatment.

Baseline values are those measured at last evaluation prior to administration of study drug in each treatment period.

Change from baseline to time point t, denoted Change_t, will be calculated as:

$$\text{Change}_t = \text{Value}_t - \text{Value}_{\text{Baseline}}$$

6.3.6 Electrocardiogram

ECG parameters, including the RR interval (intra-beat interval), PR interval (the period that extends from the beginning of the P wave [the onset of atrial depolarization] until the beginning of the QRS complex [the onset of ventricular depolarization]), QRS duration, and QT interval (the corrected QT interval is the measure of the time between the start of the Q wave and the end of the T wave in the heart's electrical cycle), will be measured according to the study assessment schedule as specified in Section 3.6. Each ECG will be assessed by the Investigator for signs of ischemia, clinically significant hypertrophy, and clinically significant T-wave (repolarization of the ventricles) abnormalities. Baseline ECGs will be defined as the last evaluation performed prior to the administration of study drug in each treatment period.

ECG changes from baseline will be summarized by treatment.

Change from baseline to time point t, denoted Change_t, will be calculated as:

$$\text{Change}_t = \text{Value}_t - \text{Value}_{\text{Baseline}}$$

6.3.7 Physical Examination

A complete PE will include measurement of body weight and height (height will be measured only at screening), general assessment of all body systems including the skin, head, eyes, ears, nose, throat, neck, lungs, heart, abdomen, lymph nodes, and extremities.

Physical examination results will be presented in individual subject data listings.

6.3.8 Pregnancy Test

Only pregnancies considered by the investigator as related to study treatment (e.g., resulting from an interaction between study drug and a contraceptive medication) are considered AEs unto themselves.

6.3.9 Concomitant Medications/Treatments

Concomitant medications administered at the time of randomization and during the study will be recorded on the CRF. The medication name, indication, dose, unit, frequency, route of administration, date(s) of administration and reason for administration will be recorded. This documentation should continue until discharge from the study.

A concomitant medication is any medication the subject enters the trial taking and is expected to continue taking for some portion of the trial, as well as any medication other than the investigational product that the subject takes during the course of the trial. All prescription and over-the-counter (OTC) medications (non-prescription drugs), including vitamins and herbal supplements, that subjects receive during the trial must be documented on the CRF. This documentation will continue until the subjects are discharged.

Concomitant medications will be coded using the World Health Organization Drug Dictionary (WHO-DD).

All prior and concomitant medication will be presented in individual subject data listings.

For medications with incomplete dates, imputation will be used to convert to a complete date. Imputed dates will be used to determine Study Day.

Partial medication start dates will be imputed as follows:

1. Only the year is reported: If the subject started to receive study drug in the year reported, then the date of the first dose of study drug will be used as the starting date of the medication. Otherwise, January 1 will be used as the start of the medication.
2. The month and year is reported: If the subject started to receive study drug during the month and year reported, then the date of first dose of study drug will be used as the starting date of the medication. Otherwise, the first day of the month will be used as the start of the medication.

Partial medication end dates will be imputed for non-ongoing medications as follows:

1. Only the year is reported: If the subject stopped to receive study drug in the year reported, then the date of the last dose of study drug will be used as the end date of the medication. Otherwise, December 31 will be used as the end of the medication.
2. The month and year is reported: If the subject stopped to receive study drug during the month and year reported, then the date of last dose of study drug will be used as the end date of the medication. Otherwise, the last day of the month will be used as the end of the medication.

The above rules are subject to logical sense, for example, imputed start date should be on or prior to imputed end date.

Verbatim terms will be coded and assigned a preferred (PT) term and an ATC (anatomic therapeutic class) term.

7. PHARMACOKINETIC/PHARMACODYNAMIC ANALYSES

7.1 General Considerations

The PK Population will be used for PK analyses. The PD Population will be used for PD analyses.

Statistical and PK analyses will be performed by Everest Clinical Research. Statistical analysis will be performed using Statistical Analysis Software SAS for Windows[®] (SAS Institute Inc., USA). Non-compartmental analysis (NCA) will be performed using Phoenix[®] WinNonlin[®] 6.4 (Certara, USA).

7.2 Pharmacokinetic Analyses

From the plasma concentration-time data, the following PK parameters will be estimated for each subject where feasible.

Table 7. Pharmacokinetic Parameters

Pharmacokinetic Parameters	
C_{\max}	Maximum observed plasma concentration
T_{\max}	Time of maximum observed plasma concentration
λ_z	Terminal elimination phase rate constant
$T_{1/2}$	Apparent terminal elimination half life
CL/F	Apparent oral clearance
V_z/F	Apparent volume of distribution
AUC_{0-t}	Area under the plasma concentration-time curve from time 0 to time t (time of last quantifiable plasma concentration)
$AUC_{0-\infty}$	Area under the plasma concentration-time curve from time 0 to infinity

C_{\max} and T_{\max} will be obtained directly from experimental observations. If multiple maxima occur at equal concentrations, the first temporal value will be taken.

The apparent terminal elimination half-life, $T_{1/2}$, where determinable, will be calculated as the natural log of 2 divided by the terminal phase rate constant, λ_z . The number of data points included in the regression will be determined by visual inspection, but a minimum of three data points in the terminal phase, excluding C_{\max} , is required to estimate λ_z . In order for the selection to take place the adjusted r^2 value reported in Phoenix[®] WinNonlin[®] must be ≥ 0.7 .

AUC_{0-t} and $AUC_{0-\infty}$ will be calculated using the linear trapezoidal linear interpolation method, using actual elapsed time values. If the actual collection time is unknown the nominal collection time may be used for the purposes of PK parameter estimation. For the purpose of calculating AUC, all missing values will be treated as missing in the PK analysis and excluded from analysis except when they occur at pre-dose where they will be set to zero. All values that were below the limit of quantitation (BLOQ) prior to T_{\max} will be set to zero. BLOQ values that occur after T_{\max} will be set to missing. When ≥ 2 consecutive plasma concentrations below the limit of quantitation (BLOQ) are encountered after T_{\max} , these and all subsequent values will be excluded from the analysis.

$AUC_{0-\infty}$ will be calculated as outlined below:

$AUC_{0-\infty} = AUC_{last} + (C_{last} / \lambda_z)$, where C_{last} is the last temporal quantifiable plasma concentration corresponding to T_{last} .

The proportion of $AUC_{0-\infty}$ due to extrapolation (AUC_{extr}) will be calculated and expressed as a percentage. $AUC_{0-\infty}$ values will be considered unreliable estimates if the AUC_{extr} is greater than 20% and will be excluded from summary tables but will be listed.

CL/F will be calculated as $Dose/AUC_{0-\infty}$.

V_z/F will be calculated as $Dose/(\lambda_z \times AUC_{0-\infty})$.

$T_{1/2}$ will be calculated as $0.693/\lambda_z$.

Descriptive statistics for the plasma concentrations of bexagliflozin by Treatment and Timepoint will be provided. Listings of plasma concentrations by Subject Number, Treatment Sequence/Treatment, Period, and Timepoint will also be provided.

To assess the effect of co-administration of exenatide on the PK of bexagliflozin, an analyses of variance (ANOVA) using a linear mixed-effects model will be fitted to the natural logarithmic transformation of PK parameters of bexagliflozin (C_{max} , AUC_{0-t} and $AUC_{0-\infty}$). The linear mixed-effects model will include subject as a random effect, and treatment, period, and sequence as fixed effects. The 90% confidence intervals (CIs) will be constructed for the ratio of the least squares (LS) geometric means of PK parameters (C_{max} , AUC_{0-t} and $AUC_{0-\infty}$), when bexagliflozin is dosed in combination with exenatide versus when dosed alone, with 80-125% defined as the lack of interaction boundaries.

The ratios of geometric least squares means and corresponding 90% CI for the treatment comparison will be determined by exponentiating the mean differences between treatments on the logarithm scale. The intra-subject geometric CV%, $100\% * \sqrt{\exp(residual) - 1}$, where residual = the residual variance component and where exp is the natural exponential function, will be reported.

The appropriateness of the mixed model will be assessed through residual analyses. Any modifications required due to poor fit will be reported and executed.

Descriptive statistics for the PK parameters C_{max} , T_{max} , $AUC_{0-\infty}$, AUC_{0-t} , CL/F, V_z/F , λ_z , and $T_{1/2}$ will be tabulated by treatment. Means, standard deviations (SD), medians, ranges (minimum; maximum), and geometric means and coefficients of variation (CV) will be presented for all PK parameters with the exception of T_{max} . Medians and ranges will be presented for T_{max} .

A listing of derived PK parameters by Subject Number, Treatment Period, and Treatment will be provided.

Refer to Appendix 2 for the SAS code.

7.3 Pharmacodynamic Analyses

Urinary glucose excretion will be determined as a PD parameter at baseline and up to 48 hours.

Descriptive statistics of glucose concentrations, creatinine concentrations, UGE, and urinary glucose/urinary creatinine will be summarized by Treatment and Timepoint.

The quantity of glucose excreted in urine will be determined by multiplying the urine glucose concentration for each time interval by the volume of urine collected for the corresponding collection interval. The total 24-hour and 48-hour quantity of glucose excreted in urine will be calculated by adding the amounts collected during each interval.

PD data will also be reported in listings.

The PD parameters, UGE and UGE normalized by urinary creatinine, including $UGE_{t_1-t_2}$, in 12 hour and 24 hour increments, and total 24-hour and 48-hour UGE, will be determined. $UGE_{t_1-t_2}$ (g) will be derived from urine volume ($V_{t_1-t_2}$, mL) x glucose concentration (mg/dL)/100/1000.

UGE normalized by urinary creatinine will be derived by dividing the UGE for each interval by the corresponding urinary creatinine concentration.

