6.6.2.3 Urine Collection for PD (UGE)

Pre-dose urine samples must be collected from -12 to 0 h for baseline measurement of UGE. Post-dose urine will be collected without preservative in four batches: 0 to 12 h, 12 to 24 h, 24 to 36 h, and 36 to 48 h collections. Urine must be refrigerated at 2 to 8°C during collection. After collection, the total volume of each batch and collection time will be recorded. Aliquots will be prepared from well mixed collections for the PD of bexagliflozin.

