6.8 Pharmacodynamic Assessment

Urinary glucose excretion (UGE) will be determined as the PD parameter. Urinary creatinine will be determined to calculate the creatinine normalized UGE.

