9.6 Pharmacodynamic Assessments

UGE and urinary creatinine will be assessed before first dosing and at the end of each treatment period.

UGE, including UGE_{t1-t2} and the total 0-24, 24-48 and 0-48 h UGE, will be determined. UGE_{t1-t2} (mg) will be derived from urine volume (V_{t1-t2}, mL) × glucose concentration (mg/dL) ÷ 100. Parameters normalized for urinary creatinine excretion will also be determined. UGE_{0-12h}, UGE_{12-24h}, UGE_{24-36h}, UGE_{36-48h} and the total 48 h UGE will be listed and presented in by subject listing and in summary tables for each group.

UGE in 12 h intervals up to 48 h post-dose, including the baseline, will be graphically presented against the corresponding treatment, bexagliflozin alone, and combination with exenatide.

The descriptive statistics will be used to describe any differences in UGE values between treatment groups.

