10. CHANGES FROM METHODS PLANNED IN THE PROTOCOL

Any changes to methods planned in this SAP will be documented in a revision to this statistical plan prior to database lock, or identified in the clinical study report.

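### SAP 7.3 divides a glucose amount by a creatinine concentration, so creatinine-normalized UGE stays proportional to urine volume

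*SAP*

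**What the plan says.** SAP 7.3 names two derived pharmacodynamic quantities: "The PD parameters, UGE and UGE normalized by urinary creatinine". It obtains UGE in grams for an interval as urine volume (mL) × glucose concentration (mg/dL) / 100 / 1000. For the longer periods it says: "The total 24-hour and 48-hour quantity of glucose excreted in urine will be calculated by adding the amounts collected during each interval".

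The normalization rule is: "UGE normalized by urinary creatinine will be derived by dividing the UGE for each interval by the corresponding urinary creatinine concentration". The same section also plans a third item, with no formula: "Descriptive statistics of glucose concentrations, creatinine concentrations, UGE, and urinary glucose/urinary creatinine will be summarized by Treatment and Timepoint".

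Protocol 9.6 describes the normalization differently: "Parameters normalized for urinary creatinine excretion will also be determined". Protocol 6.8 gives the purpose of the creatinine measurement: "Urinary creatinine will be determined to calculate the creatinine normalized UGE". Protocol 6.6.2.3 provides for the volumes: "After collection, the total volume of each batch and collection time will be recorded".

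**The concern.** Creatinine normalization is useful because dividing one excreted amount by another over the same collection removes urine volume, and with it dilution and incomplete collection. The SAP's numerator is an amount and its denominator is a concentration. Volume therefore remains in the result, whose unit is g per (mg/dL) rather than g/g.

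Three consequences follow.

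- The SAP's derivation departs from the excretion basis in Protocol 9.6.
- If the separate glucose/creatinine item is read as a concentration ratio, the SAP reports two creatinine-normalized indices that differ by the factor V/100,000.
- The division is defined per interval, while UGE is also required over 24 h and 48 h. The SAP does not say which creatinine concentration applies to a period made up of several 12-h batches.

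At stake is a descriptive comparison of bexagliflozin with and without exenatide. A difference in urine volume between treatments could be read as a difference in normalized glucosuria, or could mask one.

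**Working it through.** **Inputs from the documents.** The UGE formula and the division rule are in SAP 7.3, and the excretion basis is in Protocol 9.6. The documents give no urine volumes, glucose amounts or creatinine amounts, so every number below is an illustrative assumption. SAP 7.3 does not state the creatinine unit. I use mg/dL; another unit would only rescale the index.

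**Step 1: raw UGE is right.** With V = 1000 mL and glucose 1000 mg/dL, Protocol 9.6 gives 1000 × 1000 / 100 = 10,000 mg, and SAP 7.3 gives 1000 × 1000 / 100 / 1000 = 10 g. The two agree.

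**Step 2: algebra of the normalized index.** Let Cg and Cc be the glucose and creatinine concentrations (mg/dL).

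- SAP rule: (V × Cg / 100,000) / Cc = (V/100,000) × Cg/Cc, which is proportional to V.
- Excretion basis: (V × Cg / 100,000) / (V × Cc / 100,000) = Cg/Cc, from which V cancels (g/g).

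This holds whatever the data.

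**Step 3: effect on a treatment comparison, one batch.** Assume 10 g glucose and 0.6 g creatinine per 12-h batch under both treatments, with 1000 mL on bexagliflozin alone. Then Cc = 60 mg/dL and the SAP index alone is 10/60 = 0.167. At 1200 mL on the combination, Cc = 600 mg / 12 dL = 50 mg/dL and the index is 10/50 = 0.200.

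| Combination volume (mL) | SAP index, g per (mg/dL) | Ratio to alone (SAP) | Amount/amount (g/g) | True ratio |
|---|---|---|---|---|
| 700 | 0.117 | 0.70 | 16.7 | 1.00 |
| 800 | 0.133 | 0.80 | 16.7 | 1.00 |
| 900 | 0.150 | 0.90 | 16.7 | 1.00 |
| 1100 | 0.183 | 1.10 | 16.7 | 1.00 |
| 1200 | 0.200 | 1.20 | 16.7 | 1.00 |
| 1300 | 0.217 | 1.30 | 16.7 | 1.00 |

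Raw UGE is 10.0 g in every row.

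**Step 4: incomplete collection.** Assume a well-mixed 1500 mL batch containing 20 g glucose and 0.8 g creatinine, so Cc = 800 mg / 15 dL = 53.3 mg/dL. With 100%, 80% and 50% of the urine retained, UGE is 20, 16 and 10 g. The SAP index is 0.375, 0.300 and 0.1875, falling in step with the loss. The amount/amount ratio stays at 25.0 g/g.

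**Step 5: intervals of two batches.** Use relative units: creatinine excretion 1 in each batch, volumes 1+d and 1−d, glucose 1+e and 1−e. Three readings of the SAP rule are possible.

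- Sum of the batch indices: (1+e)(1+d) + (1−e)(1−d) = 2(1+ed).
- Summed UGE over the mean of the two concentrations: 2 / [1/(1−d²)] = 2(1−d²).
- Summed UGE over the pooled concentration: 2/1 = 2.

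Largest reading divided by smallest:

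| | e = −0.5 | e = 0 | e = 0.5 |
|---|---|---|---|
| d = 0 | 1.00 | 1.00 | 1.00 |
| d = 0.2 | 2/1.80 = 1.11 | 2/1.92 = 1.04 | 2.20/1.92 = 1.15 |
| d = 0.4 | 2/1.60 = 1.25 | 2/1.68 = 1.19 | 2.40/1.68 = 1.43 |

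Equal batch volumes make the choice immaterial. Unequal volumes give differences of 4% to 15% at d = 0.2 and 19% to 43% at d = 0.4. All three readings also still scale with overall volume.

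**The case against.** The algebra is not in dispute; the case on the other side concerns weight.

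- **Consequence.** The pharmacodynamic analysis is descriptive, SAP 3.3 plans no formal hypothesis testing, and the 80–125% boundaries apply only to Cmax and the AUCs. Raw UGE is correct and is summarized alongside glucose and creatinine concentrations, so a discordant index could be noticed. This stands and limits the severity.
- **A volume-free index may already be planned.** The glucose/creatinine item is listed straight after the two concentrations, and its natural reading is their ratio. For a single batch that equals the excretion-based ratio. This is a fair mitigation, but the item has no formula, and the one explicit derivation in the section is the wrong one.
- **The protocol conflict rests on one word.** Protocol 9.6 says excretion but gives no formula. True, but the volume dependence does not rely on that word.
- **SAP Section 10 proves little.** Its heading concerns changes from the protocol, but it only says how future changes to the SAP will be recorded: "Any changes to methods planned in this SAP will be documented in a revision to this statistical plan prior to database lock". It lists no changes at all, so its silence carries no weight here.
- **The magnitudes are assumed.** Both treatments use the same bexagliflozin dose, in confinement, under the same water rule, and nothing in the documents shows a systematic volume shift. Unsystematic differences would mainly add noise. This stands: the tables show how the error behaves, not how large it will be. Nor do the documents exclude a shift. Protocol 5.7.2 allows water as desired apart from the hour either side of dosing, and Protocol 1.2 lists nausea, vomiting and diarrhea as the most common adverse events of the class.

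**Conclusion.** The concern holds. Followed exactly, SAP 7.3 yields a creatinine-normalized UGE that is proportional to urine volume, does not correct for lost urine, and does not match the excretion basis in Protocol 9.6. I found nothing elsewhere in the two documents that corrects the sentence. The volume dependence is algebraic and needs no assumption. A between-treatment volume ratio of r gives a spurious ratio of r when glucose and creatinine excretion are equal; its actual size is unknown because no volumes are given. The multi-batch gap is an under-specification, secondary to the wrong denominator.

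This should be fixed before analysis. It affects one of the two named parameters under the pharmacodynamic half of the primary objective, but not raw UGE, the pharmacokinetic analysis or any decision boundary.

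**What to change.** Replace the normalization sentence in SAP 7.3 with wording such as:

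> Creatinine-normalized UGE (g/g) is the UGE for an interval divided by the amount of creatinine excreted in the same interval (urine volume × creatinine concentration, converted to g). For intervals spanning several batches, it is the summed UGE divided by the summed creatinine excretion.

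Also state how the separate glucose/creatinine summary is defined. Using the same definition is simplest; for a single batch it equals the concentration ratio.

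The cost is one SAP sentence, a short clarification and one line of derivation code. Batch volumes and urinary creatinine are already collected, so no new sample, visit or procedure is needed.
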